4.3 Major Protocol Deviations

All protocol deviations related to study inclusion or exclusion criteria, conduct of the trial, patient management or patient assessment will be identified and categorised as major or minor by trial management team while blinded to subject's treatment group allocation. The following protocol deviations will be categorised as major protocol deviations:

Any of the below inclusion criteria not met but subject enrolled into the study

1. Male or female outpatient of ≥ 18 years of age or \geq country's legal age for adult consent
2. Dukes C colon cancer, high risk Dukes B colon cancer, Dukes B rectal cancer or Dukes C rectal cancer
3. Undergone complete resection of primary tumour
4. Completed standard therapy (at least 3 months of chemotherapy \pm radiotherapy)
5. Written informed consent

Any of the below exclusion criteria met but subject enrolled into the study

6. Gastrointestinal bleeding within the past one year
7. Haemorrhagic diathesis (i.e. haemophilia)
8. History of recent cancers (except for colorectal cancers, non-melanoma skin cancers, basal cell carcinomas, squamous cell carcinomas) in the past 5 years
9. History of stroke, coronary arterial disease, angina, or vascular disease
10. Patient on active current treatment of antiplatelet agents (i.e. off-study Aspirin, clopidogrel, ticlopidine)
11. Patient receiving active treatment of anticoagulants (i.e. warfarin, low molecular weight heparins)

12. Patient having known allergy to NSAID or Aspirin

Others

13. Recurrence diagnosed before randomisation but subject was randomised

These major protocol deviations will be provided in two listings together with corresponding subject ID, treatment group, site, country, description and the following three major protocol deviation categories: Inclusion criteria, exclusion criteria and others. Minor protocol deviations relating to eligibility criteria will also be provided.

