10. CONCOMITANT/CONTRAINDICATED MEDICATIONS

Patients are not permitted to take the following medications concurrently with the study drug. If required, patient should be removed from the study treatment with the reason clearly documented: -

- Other investigational drugs while on treatment with study drug
- Any anticancer treatment while on treatment with study drug
- Antiplatelet agents (off-study Aspirin, clopidogrel, ticlopidine) concurrently with study medication
- Anticoagulants (warfarin, unfractionated heparin or low molecular weight heparin) concurrently with study medication

Patients should be encouraged to use paracetamol or codeine phosphate for analgesia and to avoid NSAID whenever possible. Although short term intermittent NSAID use is allowed, NSAID should not be prescribed with study drug for more than 2 consecutive weeks. The use of NSAID must be clearly documented throughout the study.

Patients will be allowed concurrent PPIs, H2 antagonists or antacids.

Ongoing concomitant medication will be recorded from baseline visit date until 30 days after treatment discontinuation. Patients receiving study drug should maintain adequate contraception.

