2 STUDY OBJECTIVES

Primary objective

Null hypothesis: Among subjects with Dukes C or high risk Dukes B colorectal cancer, Disease Free Survival (DFS) between those randomised to Aspirin and those randomised to placebo control is equal.

Alternative hypothesis: Among subjects with Dukes C or high risk Dukes B colorectal cancer, DFS between those randomised to Aspirin and those randomised to placebo is not equal.

Primary objective: To compare DFS between the group randomised to Aspirin with the group randomised to placebo control in subjects with Dukes C or high risk Dukes B colorectal cancer.

Secondary objectives

1. To compare the DFS between the group randomised to Aspirin with the group randomised to placebo control in subjects with high risk Dukes B and Dukes C colon cancer.
2. To compare the overall survival (OS) between the group randomised to Aspirin with the group randomised to placebo control in subjects with Dukes C or high risk Dukes B colorectal cancer.

Exploratory objectives

1. To compare the DFS and OS between the group randomised to Aspirin with the group randomised to placebo control in subjects with Dukes C or high risk Dukes B colorectal within the following subgroups:
 - a. Baseline variables
 - i. Country.

Countries with small sample size (less than 25) will be pooled under 'Others' or with countries with similar ethnic population.

- ii. Resected high risk Dukes B colon cancer, Dukes C colon cancer, colon cancer and rectal cancer.
- iii. Exposed to Oxaliplatin, not exposed to Oxaliplatin.
- iv. Ethnicity (East Asian, South Asian, Caucasian and Others).
- v. Type of surgery (laparoscopic surgery, open surgery).
- vi. Chemotherapy duration (<3 months, 3-6 months, >6 months).
- vii. Age group (<70, ≥70).

b. Translational variables

- i. Compliant subjects, non-compliant subjects.

Compliant subject is defined as an individual who is on the study drug for at least 70% of days in first year from randomisation or up to treatment discontinuation or recurrence, whichever is earlier.

- ii. Duration of exposure to study drug (<1 year, 1-2 years, >2 years).

The duration of exposure to study drug during the treatment period is defined as the number of days from the first dose to the last dose excluding days of interruptions, i.e. "duration of exposure" = "last dosing date" – "first dosing date" – "days off medication" + "1 day".

- iii. PIK3CA mutations (mutant PIK3CA, wild-type PIK3CA)

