4.2 Analysis Populations

All efficacy analyses will be carried out on modified intention-to-treat (mITT) basis, i.e., all subjects who signed the informed consent form for the study enrolment and commenced study treatment after the randomisation are to be analysed as randomised.

As part of sensitivity analysis, efficacy analysis on per-protocol basis will also be performed. Per-protocol analysis consists of subjects included in the mITT population after excluding those with major protocol deviation and those who were compliant <70% of the days in the first year from randomisation. Compliance has been defined in section 2.

Subjects included in safety data analysis are those who received at least one dose of the study treatment drug. These subjects will be grouped and analysed as actually treated.

The number of subjects screened, randomised to the study treatment, completing each subsequent study period including up to 3-year treatment and 5-year follow-up will be summarised in a CONSORT flow chart.

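### The SAP's list of major deviations omits prohibited aspirin, antiplatelet and prolonged NSAID use during study treatment, so adherent placebo patients who also take aspirin stay in the per-protocol set

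*SAP*

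**What the plan says.** SAP 4.3 introduces its list with "The following protocol deviations will be categorised as major protocol deviations". Items 1-5 are inclusion criteria not met. Items 6-12 come under "Any of the below exclusion criteria met but subject enrolled into the study", and item 10 among them reads "Patient on active current treatment of antiplatelet agents (i.e. off-study Aspirin, clopidogrel, ticlopidine)". Item 13, the only entry under the residual heading, is "Recurrence diagnosed before randomisation but subject was randomised".

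SAP 4.2 forms the per-protocol set from the mITT population after "excluding those with major protocol deviation and those who were compliant <70% of the days in the first year from randomisation", refers to section 2 for the meaning of compliance, and calls the per-protocol analysis part of the sensitivity analysis. SAP section 2 defines a compliant subject as one on study drug for at least 70% of days "in first year from randomisation or up to treatment discontinuation or recurrence, whichever is earlier".

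Protocol section 10 lists what may not be taken during study treatment, including "Antiplatelet agents (off-study Aspirin, clopidogrel, ticlopidine) concurrently with study medication". If such a drug is needed, the patient comes off study treatment and the reason is documented. The same section says NSAIDs should not be prescribed with study drug for more than two consecutive weeks and requires their use to be documented throughout.

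**The concern.** In a placebo-controlled trial of aspirin, a placebo patient who takes aspirin is the most direct departure from assigned treatment. The per-protocol analysis is where one expects such patients to be removed. Under the SAP's rules they are not: the deviation list looks only at entry and before randomisation, and the compliance rule looks only at study tablets. The per-protocol comparison therefore keeps whatever concurrent aspirin use there is in the placebo arm.

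The use is also hard to see in the planned output. Mock Tables 1-14 do not show off-study aspirin, antiplatelet or NSAID use by arm. The listings cover eligibility-related deviations and other major deviations, so a medication deviation graded as minor would appear in neither.

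**Working it through.** **Step 1. Does any listed item cover use after randomisation?**

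| SAP 4.3 items | Content | Timing |
|---|---|---|
| 1-5 | Inclusion criteria not met | Entry |
| 6-12 | Exclusion criteria met, including antiplatelets or off-study aspirin (item 10) | Entry |
| 13 | Recurrence already diagnosed | Before randomisation |

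No item does. The entry exclusion for long-term aspirin, NSAID or Cox-2 inhibitor treatment is also missing from the list, although item 10 covers current off-study aspirin at entry.

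**Step 2. Does the compliance rule catch concurrent use?** The numerator is days on study drug, so off-study aspirin neither adds to it nor subtracts from it. A placebo patient who takes aspirin with the tablets and reaches 70% passes. The window also covers at most the first of three treatment years, so concurrent use that starts in year 2 or 3 falls outside it however the rule is read.

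**Step 3. What happens to early stoppers?** Take a hypothetical patient who takes tablets on 108 of the first 120 days and then stops.
- Section 2, with the count ending at treatment discontinuation: 108/120 = 90%. The patient is kept.
- Section 4.2, read literally over the first year: 108/365 = 29.6%. The patient is excluded.

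Section 4.2 refers back to section 2, but the two wordings give opposite answers for the same patient. The note to mock Table 2 adds a third wording, with study discontinuation in place of treatment discontinuation.

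**Step 4. The plan's own figure.** The inputs from SAP 3.5 are HR 0.72, two-sided 5% and 80% power; allocation is 1:1 (SAP 3.1).
- Schoenfeld: 4 × (1.960 + 0.8416)² / (ln 0.72)² = 4 × 7.849 / 0.1079 = 291 events.
- Freedman: 7.849 × (1.72/0.28)² = 297 events after rounding up.

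The stated 300 reproduces and is not in dispute.

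**Step 5. Illustrative dilution.** Let c be the share of placebo patients kept in the set who receive the full aspirin effect from the start. The documents give no value for c. The apparent hazard ratio is 0.72 / (1 − c + 0.72c) = 0.72 / (1 − 0.28c).

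| c (assumed) | Apparent HR |
|---|---|
| 2% | 0.72/0.9944 = 0.724 |
| 5% | 0.72/0.986 = 0.730 |
| 10% | 0.72/0.972 = 0.741 |
| 15% | 0.72/0.958 = 0.752 |
| 20% | 0.72/0.944 = 0.763 |

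**The case against.** The best defence is that SAP 4.3 opens by having all deviations, including those of conduct and patient management, "categorised as major or minor by trial management team while blinded" to treatment group. That team could grade concurrent aspirin as major. But the next sentence states which deviations are major, without wording that leaves the list open, and no item fits. The defence shows that the right process exists, not that the rule does.

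The defence is stronger on scale. Entry excludes stroke, coronary disease, angina, vascular disease and current antiplatelet or long-term aspirin or NSAID treatment, which removes many obvious reasons to start aspirin. Contamination may be near the low end of the range. The per-protocol analysis is also only a sensitivity analysis. Both points stand and keep this minor.

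A reader might infer that a placebo patient who stops the tablets and then starts aspirin is also a missed deviation. The documents do not support that. Section 10 of the protocol concerns use concurrent with study drug, and stopping study drug when a barred medicine is needed is what it asks for. Such a patient has followed the protocol. Whether the patient stays in the set depends on the conflict in step 3 of the working. The data are also limited: general concomitant medication is recorded only until 30 days after treatment discontinuation. The NSAID field continues beyond that, but the documents do not say that it captures aspirin.

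**Conclusion.** The point holds, within limits. The stated rules keep in the per-protocol set, and class as compliant, any placebo patient who takes barred aspirin or antiplatelets, or NSAIDs beyond the two-week limit, alongside study drug while at least 70% adherent. This affects the per-protocol sensitivity analysis and the exploratory compliance subgroup. It does not affect the mITT primary analysis, the 300 events or the 1587 patients.

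The size cannot be derived from the documents. The range 0.724-0.763 for a true 0.72 rests on an assumed 2-20% of placebo patients and on an immediate, full effect of off-study aspirin.

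Two stronger readings should be resisted. A reader might turn the diluted hazard ratio into a loss of power at 300 events. That describes the primary comparison under an unsupported contamination rate, and changing the per-protocol definition would not alter it. A reader might also conclude that the per-protocol analysis is of no help with a null result. It still removes ineligible and poorly adherent patients, and the SAP separately reports exposure-duration subgroups and reasons for discontinuation by arm.

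**What to change.** Before unblinding:

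1. Add to the SAP 4.3 list, for blinded classification, off-study aspirin or other antiplatelet use concurrent with study drug, and NSAID use with study drug beyond the limit in protocol section 10. Confine both to the time on study drug.
2. Add a table by arm of recorded off-study aspirin or antiplatelet use and of NSAID use. State that non-NSAID medication is captured only until 30 days after treatment discontinuation, and say in which field off-study aspirin is recorded.
3. Reconcile the compliance window in SAP 4.2, SAP section 2 and the note to mock Table 2, so that it is settled whether early stoppers are kept.

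The cost is SAP wording and one table, using medication data the protocol already collects during treatment. The sample size, alpha and primary analysis stay as they are. The downside is that excluding patients on a post-randomisation event can select between arms, so the per-protocol analysis must remain a sensitivity analysis. The table carries no such risk. An analysis that censors at the start of off-study aspirin is not needed here: the censoring may be informative, for example if aspirin follows a vascular event.

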4.4 Discontinuation and Exposure to Study Treatment

Numbers and percentages of subjects who permanently discontinued the study drug will be presented by randomised treatment group. Reasons for treatment discontinuation will be summarised together with follow up completion rate and time. Duration of exposure to study drug will be further summarised using descriptive statistics by group. Definition of duration of exposure can be found in section 2.

4.5 Demographics and Baseline Characteristics

Demographics and baseline characteristics including details of colorectal cancer, adjuvant therapy, risk factors, medical and family history, vital signs, and laboratory investigations for the subjects will be summarised using descriptive statistics. No significance tests will be performed for between groups comparison. Clinical comparability will be assessed based on only the summary statistics presented.

4.6 Time-to-event Endpoints

For primary outcome of DFS, survival curves will be constructed using the Kaplan-Meier method. Product-limit estimates of 3- and 5-year survival rates will be calculated. Median survival times will also be reported. The complementary log-log transformation will be used for deriving the median survival times corresponding 95% CIs. The primary analysis will be a mITT analysis which uses stratified logrank test adjusting for trial stratification factor

(centre pooled by country (categorical), type of tumour (Dukes C colon vs. high risk Dukes B colon vs. rectal; categorical) and type of adjuvant chemotherapy (exposed vs. not exposed to Oxaliplatin; categorical)) to generate p-value comparing the treatment groups, followed by multivariate Cox proportional hazard (PH) regression model to estimate adjusted HR and its corresponding 95% CI. The multivariate Cox PH regression model will also include the trial stratification factors used in the stratified logrank test as covariates. Additional covariates such as time from surgery to first chemotherapy in days (continuous), type of surgery (laparoscopic surgery vs. open surgery; categorical), chemotherapy duration (<3 months vs. 3-6 months vs. >6 months; categorical) and age group (<70 vs. ≥ 70 years old; categorical) will be added as part of sensitivity analysis. The CI of the HR will be based on profile-likelihood. Firth's correction may be used if monotone likelihood phenomenon is observed. Unadjusted HR and p-value from non-stratified logrank test will also be reported as supplementary results.

As part of secondary objective, the same analysis on DFS will be repeated for sub-population of colon cancer except that the covariate, type of tumour, will consist of only two categories: Dukes C colon vs. high risk Dukes B colon.

The secondary outcome of OS will be analysed in a similar manner as the primary endpoint, except that repeated analysis on colon cancer sub-population will not be done.

For all subgroup analyses of DFS and OS by different countries, tumour types (high risk Dukes B colon, Dukes C colon, colon, rectal), adjuvant chemotherapy types (exposed to Oxaplatin, not exposed to Oxaliplatin), ethnic groups (East Asian, South Asian, Caucasian, Others), type of surgery (laparoscopic surgery, open surgery), chemotherapy duration (<3 months, 3-6 months, >6 months), age group (<70, ≥ 70), levels of compliance (<70%, $\geq 70\%$), duration of exposure to drug (<1 year, 1-2 years, >2 years), PIK3CA mutations (mutant PIK3CA, wild-type PIK3CA) and COX-2 expression (positive for COX-2 overexpression, negative for COX-2 overexpression), tests for interactions between treatment group and the subgroup variable of interest will be conducted first. As the subgroups under tumour types are not mutually exclusive, the test for interaction will be based on the original mutually

exclusive groups. Results of subgroup analyses will be presented in forest plots. Subgroup analyses will be considered as exploratory.

Appropriateness of Cox PH regression model will be checked using graphical method of log-log survival curves for treatment indicator and each covariate. Continuous covariate will be dichotomised at mean value to check for the PH assumption. PH assumption will be considered not satisfied if there is strong evidence of non-parallelism in the log-log survival curves. Should there be at least one covariate not satisfying the PH assumption, “no-interaction” (i.e. estimated coefficients not varying by stratum) stratified Cox regression model will be used instead. The model will be stratified by strata formed after combining categories of all covariates which did not satisfy the PH assumption. Covariate(s) which satisfies the PH assumption will remain included in the stratified model. If the treatment indicator is found to not satisfy the PH assumption, time-varying HR will be obtained by partitioning the follow-up time into 1-year intervals.

In addition, cumulative incidence curves for recurrence free survival will be estimated for the two treatment groups after considering competing risks of death due to other cancers and death due to other causes. Recurrence free survival is defined as time from randomisation to first disease recurrence. The cumulative incidence curves will be constructed for first disease recurrence using Fine and Gray’s model, adjusting for the trial stratification factors (centre pooled by country (categorical), type of tumour (Dukes C colon vs. high risk Dukes B colon vs. rectal; categorical) and type of adjuvant chemotherapy (exposed vs. not exposed to Oxaliplatin; categorical)). Cause-specific sub-distribution hazard ratios together with its corresponding 95% CIs will also be reported.

For all the survival analyses performed, Breslow’s method will be used for handling of ties.

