12.2 Statistical analysis

All statistical analyses will be carried out on an intention-to-treat basis.

In the analysis of disease free survival, an event of interest is considered to have occurred if a patient relapses or dies during the study period. The starting point for disease free survival is the date of randomisation and the end point is the date of first disease recurrence or date of death, whichever occurs first. Patients in whom there has been no evidence of disease after treatment are censored at the date of last follow-up. Similarly, the overall survival time is censored at the date when the patient is last known to be alive.

Each primary endpoint will be analysed as follows. Survival curves will be constructed using the Kaplan-Meier method. Life table estimates of 3 and 5 year survival rates will be calculated. The efficacy of Aspirin will be evaluated by the Hazard Ratio (HR) and its corresponding 95% CI. A Cox proportional hazard model will be used to estimate HRs adjusting for the trial stratification factors (site, type of tumour and type of adjuvant chemotherapy). Stratified analysis and other non-proportional hazard models (which allow for the effects of covariates to vary over time) would be considered when proportional hazards assumption is not valid.

The secondary endpoint of overall survival will be analysed in a similar manner to the primary endpoints. For the subgroup analyses, tests for interaction for the colon cancer subgroups and other subgroups will be conducted first. Similar analyses of DFS and OS as presented above will be repeated within the subgroups respectively defined by ethnicity, tumour type, and patients'

compliance and according to patient's PIK3CA mutational status. The percentage of patients with different PIK3CA mutational status will be compared by Chi-square test in the Aspirin and Placebo groups.

As an exploratory analysis, cumulative incidence function will be estimated and the two treatment arms will be compared using Gray's method when considering competing risks of first recurrence with different causes of death due to colorectal cancer, other cancers or other causes.

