- iv. COX-2 expression (positive for COX-2 overexpression, negative for COX-2 overexpression)

2. To compare the recurrence free survival between the group randomised to Aspirin with the group randomised to placebo control in subjects with Dukes C or high risk Dukes B colorectal cancer, taking into account competing risks of death due to other cancers and death due to other causes.

Subgroup analyses on PIK3CA mutations and COX-2 are restricted to subjects from Australia, New Zealand, Taiwan (Shuang Ho Hospital), Singapore (National Cancer Centre)

and Malaysia (University Malaya Medical Centre) sites who consented to tumour sample collection.

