3 STUDY ENDPOINTS

Primary endpoint

DFS is defined as the time from randomisation to the time of documentation of first disease recurrence or death from any cause. If there is no disease recurrence or death by the time when a subject is last followed up, it will be censored at that time.

The disease recurrence is defined as any one of the followings:

- Unequivocal radiological evidence of colorectal cancer recurrence
- Recurrence detected by digital rectal examination (DRE)
- Positive histology or cytology (i.e. peritoneal or pleural cytology)
- Colonoscopic evidence of local cancer recurrence at the previous operation site
- Detection of a new colon or rectal primary tumour

Secondary endpoints

OS is defined as the time from randomisation to the time of death from any cause. If there is no death by the time when a subject is last known to be alive, it will be censored at that time.

Exploratory endpoints

Exploratory endpoints involve DFS and OS in subgroups, as well as recurrence free survival. Recurrence free survival is defined as time from randomisation to first disease recurrence.

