
CEA, $\mu\text{g/L}$
 
n
 
Mean (SD)
 
Median (IQR)
 
Min, Max
 
Clinically significant, n (%)
	
XXX
 
XX.X (XX.X)
 
XX.X (XX.X)
 
XX.X, XX.X
 
XX (XX.X)
	
XXX
 
XX.X (XX.X)
 
XX.X (XX.X)
 
XX.X, XX.X
 
XX (XX.X)
	
XXX
 
XX.X (XX.X)
 
XX.X (XX.X)
 
XX.X, XX.X
 
XX (XX.X)
	
XXX
 
XX.X (XX.X)
 
XX.X (XX.X)
 
XX.X, XX.X
 
XX (XX.X)

n: number of subjects; %: percentage of respective population pool treatment group; SD: standard deviation; IQR: interquartile range.

Table 7: Disease free survival and overall survival

	Modified intention-to-treat		Per-protocol	
	Aspirin (N=xxxx)	Placebo (N=xxxx)	Aspirin (N=xxxx)	Placebo (N=xxxx)
First recurrence, n (%)	xxx (xx.x)	xxx (xx.x)	xxx (xx.x)	xxx (xx.x)
Site of recurrence, n (%)				
Local	xxx (xx.x)	xxx (xx.x)	xxx (xx.x)	xxx (xx.x)
Anastomotic site	xxx (xx.x)	xxx (xx.x)	xxx (xx.x)	xxx (xx.x)
Lymph node	xxx (xx.x)	xxx (xx.x)	xxx (xx.x)	xxx (xx.x)
Peritoneum	xxx (xx.x)	xxx (xx.x)	xxx (xx.x)	xxx (xx.x)
Liver	xxx (xx.x)	xxx (xx.x)	xxx (xx.x)	xxx (xx.x)
Lungs	xxx (xx.x)	xxx (xx.x)	xxx (xx.x)	xxx (xx.x)
New primary	xxx (xx.x)	xxx (xx.x)	xxx (xx.x)	xxx (xx.x)
Others	xxx (xx.x)	xxx (xx.x)	xxx (xx.x)	xxx (xx.x)
Method of first recurrence diagnosis, n (%)				
Radiological imaging	xxx (xx.x)	xxx (xx.x)	xxx (xx.x)	xxx (xx.x)
Histology / cytology	xxx (xx.x)	xxx (xx.x)	xxx (xx.x)	xxx (xx.x)
Scope	xxx (xx.x)	xxx (xx.x)	xxx (xx.x)	xxx (xx.x)
Digital rectal examination	xxx (xx.x)	xxx (xx.x)	xxx (xx.x)	xxx (xx.x)
Others	xxx (xx.x)	xxx (xx.x)	xxx (xx.x)	xxx (xx.x)
Death, n (%)	xxx (xx.x)	xxx (xx.x)	xxx (xx.x)	xxx (xx.x)
Cause of death, n (%)				

Colorectal cancer	XXX (XX.X)	XXX (XX.X)	XXX (XX.X)	XXX (XX.X)
Other cancer	XXX (XX.X)	XXX (XX.X)	XXX (XX.X)	XXX (XX.X)
Other causes	XXX (XX.X)	XXX (XX.X)	XXX (XX.X)	XXX (XX.X)
Unknown	XXX (XX.X)	XXX (XX.X)	XXX (XX.X)	XXX (XX.X)
Presence of colon/rectal cancer at death, n (%)				
Yes	XXX (XX.X)	XXX (XX.X)	XXX (XX.X)	XXX (XX.X)
No	XXX (XX.X)	XXX (XX.X)	XXX (XX.X)	XXX (XX.X)
Unknown	XXX (XX.X)	XXX (XX.X)	XXX (XX.X)	XXX (XX.X)
Median follow-up time (95% CI), month	XX.X (XX.X-XX.X)	XX.X (XX.X-XX.X)	XX.X (XX.X-XX.X)	XX.X (XX.X-XX.X)
All tumour types				
Subjects with recurrence or who died without recurrence, n (%)	XXX (XX.X)	XXX (XX.X)	XXX (XX.X)	XXX (XX.X)
Median DFS time (95% CI), month	XX.X (XX.X-XX.X)	XX.X (XX.X-XX.X)	XX.X (XX.X-XX.X)	XX.X (XX.X-XX.X)

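### SAP 4.6 gives no competing state to colorectal-cancer deaths without recorded recurrence, or to deaths of unknown cause, so a literal reading would censor the former and possibly the latter

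*SAP*

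**What the plan says.** - **Event of interest.** SAP section 3 states: "Recurrence free survival is defined as time from randomisation to first disease recurrence". Its list of what counts as recurrence covers radiology, digital rectal examination, histology or cytology, colonoscopy at the operation site, and finally "Detection of a new colon or rectal primary tumour". Death, from colorectal cancer or otherwise, is not on the list.
- **Competing events in the SAP.** The exploratory objective in section 2 compares recurrence free survival "taking into account competing risks of death due to other cancers and death due to other causes". Section 4.6 names the same two causes: the cumulative incidence curves are estimated "after considering competing risks of death due to other cancers and death due to other causes".
- **Competing events in the protocol.** Section 12.2 plans an exploratory analysis of "competing risks of first recurrence with different causes of death due to colorectal cancer, other cancers or other causes", which is three causes of death.
- **Causes of death collected.** In mock Table 7 (SAP Appendix 1), the block headed "Cause of death, n" has four categories: colorectal cancer, other cancer, other causes and unknown.
- **Censoring.** SAP section 3 gives censoring rules for DFS and OS, and none for recurrence free survival.

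**The concern.** Two of the four collected causes of death have no named state in the model. For a patient with a recorded recurrence before death this does not matter, because the recurrence is the first event. The gap concerns patients whose first event is death.

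Such patients are plausible. Protocol 11.3 makes surveillance CT and colonoscopy optional at centre level and allows alternate 3-monthly assessments by phone. Protocol 11.6 does not accept a raised CEA or abnormal liver function as evidence of recurrence. After month 60, data come from record review or phone contact (protocol 11.8).

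A programmer who codes only the listed states would censor these patients at death. Censoring assumes that the patient remains at risk of recurrence after that date, which is the error that competing-risk methods are meant to avoid. Recurrences plus competing deaths would then no longer add up to the DFS events, which include death from any cause.

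**Working it through.** **The plan's own event figure.** With HR 0.72, two-sided 5% and 80% power (SAP 3.5):

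- Schoenfeld: 4 × (1.960 + 0.842)² / (ln 0.72)² = 291 events.
- Freedman: (1.960 + 0.842)² × (1.72/0.28)² = 297 events.
- From the sample size: 1587 × 0.90 × 0.21 = 299.9 events.

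The stated 300 reproduces. It serves below only as the base for the assumed shares.

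**States compared**

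| Death without recorded recurrence, by cause | Protocol 12.2 | SAP 2 and 4.6 | SAP Table 7 |
|---|---|---|---|
| Colorectal cancer | named | not named | collected |
| Other cancer | named | named | collected |
| Other causes | named | named | collected |
| Unknown | not named | not named | collected |

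**Illustration of size.** From the documents: pooled 5-year DFS of 79%. Assumed, because the documents give no figures: constant cause-specific hazards; a share u of first events that are deaths with no named state (1%, 5% or 10%, that is 3, 15 or 30 of 300); and a share o that are deaths in the two named causes (5%, 10% or 15%). Recurrence makes up the remaining 1 − o − u.

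Five-year cumulative incidence of recurrence under each coding:

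- Competing: (1 − o − u) × 0.21
- Censored: [(1 − o − u)/(1 − u)] × (1 − 0.79^(1 − u))
- Event: (1 − o) × 0.21

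Example with o = 10% and u = 5%:

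- Competing: 0.85 × 0.21 = 17.85%
- Censored: (0.85/0.95) × (1 − 0.79^0.95) = 0.8947 × 0.2006 = 17.95%
- Event: 0.90 × 0.21 = 18.90%

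| o | u | Competing | Censored | Event | Competing − censored | Event − censored |
|---|---|---|---|---|---|---|
| 5% | 1% | 19.74 | 19.76 | 19.95 | −0.02 | +0.19 |
| 5% | 5% | 18.90 | 19.01 | 19.95 | −0.11 | +0.94 |
| 5% | 10% | 17.85 | 18.05 | 19.95 | −0.20 | +1.90 |
| 10% | 1% | 18.69 | 18.71 | 18.90 | −0.02 | +0.19 |
| 10% | 5% | 17.85 | 17.95 | 18.90 | −0.10 | +0.95 |
| 10% | 10% | 16.80 | 16.99 | 18.90 | −0.19 | +1.91 |
| 15% | 1% | 17.64 | 17.66 | 17.85 | −0.02 | +0.19 |
| 15% | 5% | 16.80 | 16.90 | 17.85 | −0.10 | +0.95 |
| 15% | 10% | 15.75 | 15.93 | 17.85 | −0.18 | +1.92 |

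**Check on adding up** (o = 10%, u = 5%). Under censoring, recurrence plus the two named competing causes total 1 − 0.79^0.95 = 20.06%, against a DFS failure of 21%. Under competing coding the parts are 17.85 + 2.10 + 1.05 = 21.00%, which agrees.

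**The case against.** The best defence is that the SAP nowhere says that these deaths are censored. A reader might infer that it does, but the text is silent. An analyst could place unknown-cause deaths under other causes, or treat a colorectal-cancer death as evidence of recurrence. The first is a fair reading, which is why unknown-cause deaths are only possibly affected. The second conflicts with the SAP's own recurrence criteria, which do not include death. So for colorectal-cancer deaths the listed states, applied as written, leave only censoring.

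Recurrence is also asked about at every scheduled assessment to month 60, and yearly afterwards for consenting patients. That limits the number of such deaths but does not exclude them.

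Three stronger readings are tempting and should be resisted:

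- **That the SAP specifies the wrong model.** The phrase "Cause-specific sub-distribution hazard ratios" combines the names of two different quantities. However, the Table 7 rows are labelled as sub-distribution hazard ratios for first recurrence and for death due to other cancers, with p-values from the Fine and Gray model. The natural meaning is one sub-distribution hazard ratio per cause, so this is loose wording.
- **That nothing else separates recurrence from death.** Table 7 reports first recurrence, death, cause of death and presence of colorectal cancer at death by arm, and OS is analysed separately.
- **That all these deaths are missed recurrences, so that recurrence is understated.** The documents do not show this, and the direction of the shift depends on the coding. Coding unknown-cause deaths as competing lowers the estimate, while counting colorectal-cancer deaths as events raises it.

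**Conclusion.** The point holds as a gap in the SAP's list of competing events and an unexplained departure from protocol 12.2. Taken literally, the list mishandles colorectal-cancer deaths without recorded recurrence; for unknown-cause deaths the handling is undefined.

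The consequence is small. Relative to censoring, 5-year recurrence incidence would be about 0.02–0.20 points lower under competing coding, or about 0.2–1.9 points higher under event coding. Both ranges depend on the assumed 1–10% share of first events and on constant hazards. The illustration is pooled over arms, so it says nothing about bias in the treatment comparison.

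A reader might also infer a threat to the main result. There is none: the analysis is exploratory, DFS counts death from any cause, and OS counts every death.

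**What to change.** In SAP 4.6, and in the matching objective in section 2, state that every death without prior recorded recurrence is a competing event. Restore colorectal-cancer death as a third cause, in line with protocol 12.2, and assign unknown-cause deaths to a competing state, so that all four Table 7 categories have a place. This leaves the recurrence definition unchanged.

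Add one sensitivity analysis that counts colorectal-cancer deaths without recorded recurrence as recurrence at the date of death. It belongs in a sensitivity analysis because, as the main rule, it would add a criterion to the endpoint definition in SAP section 3.

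The cost is one coding rule and one extra run, using data already collected.
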